10.1.8. Source Documents

- Source documents is in this clinical investigation considered prior medical records, including the documentation for the diagnosis of PF (CT report), used to enter relevant medical history details (not applicable for the pilot part of the investigation).
- Majority of the clinical data in this clinical investigation will be entered directly into the CRF and no source data verification will be performed.
- Data reported entered in the site assessment CRF system that are transcribed from source documents must be consistent with the source documents or the discrepancies must be explained.
- Definition of what constitutes source data, and its origin can be found in the monitoring plan.

10.1.9. Clinical Investigation and Site Start and Closure

First Act of Recruitment

The clinical investigation start date is the date on which the clinical investigation will be open for recruitment of subjects.

The first act of recruitment is the first site open and will be the clinical investigation start date.

Clinical investigation/Site Termination

The sponsor or designee reserves the right to close the clinical investigation site or terminate the clinical investigation at any time for any reason at the sole discretion of the sponsor. Clinical investigation sites will be closed upon clinical investigation completion. A clinical investigation site is considered closed when all required documents and have been collected and a clinical investigation-site closure visit has been performed.

The investigator may initiate clinical investigation-site closure at any time, provided there is reasonable cause and sufficient notice is given in advance of the intended termination.

Reasons for the early closure of a clinical investigation site by the sponsor or investigator may include but are not limited to:

For clinical investigation termination:

• Discontinuation of further device development.

For site termination:

- Failure of the investigator to comply with the CIP, the requirements of the IRB or local health authorities, the sponsor's procedures, or GCP guidelines.
- Inadequate or no recruitment (evaluated after a reasonable amount of time) of subjects by the investigator.
- Total number of subjects included earlier than expected.

If the clinical investigation is prematurely terminated or suspended, the sponsor shall promptly inform the investigators, the IRBs, the regulatory authorities, and any contract research organization(s) used in the clinical investigation of the reason for termination or suspension, as specified by the applicable regulatory requirements. The investigator shall promptly inform the subject and should assure appropriate subject therapy and/or follow-up.

10.1.10. Publication Policy

- The primary publication should be published by the sponsor prior to any other investigator-initiated publications, manuscripts, abstracts, or presentations.
- The results of this clinical investigation may be published or presented at scientific meetings. If this is foreseen, the investigator agrees to submit all manuscripts or abstracts to the sponsor before submission. This allows the sponsor to protect proprietary information and to provide comments.
- The sponsor will comply with the requirements for publication of clinical investigation results. In accordance with standard editorial and ethical practice, the sponsor will generally support publication of multicenter studies only in their entirety and not as individual site data. In this case, a coordinating investigator will be designated by mutual agreement.
- Authorship will be determined by mutual agreement and in line with International Committee of Medical Journal Editors authorship requirements.

10.2. Appendix 2: AEs, ADEs, SAEs and SADEs: Definitions

10.2.1. Definition of AE

AE Definition

An AE is any untoward medical occurrence, unintended disease or injury, or untoward clinical signs (including laboratory finding) in subjects (i.e., participants in the clinical investigation), users or other persons, whether or not related to the investigational medical device and whether or not anticipated or unanticipated.

Notes:

 Includes events related to the investigational medical device or the comparator, and the procedures involved

Comparator is used in the control group and can be:

- Medical device
- Therapy (e.g., active treatment, normal clinical practice)
- Placebo
- No treatment

Lack of efficacy per se will not be reported as an AE or SAE. Such instances will be captured in the efficacy assessments.

AEs, not fulfilling the definition of an ADE, SAE, and SADE, should only be reported if they are related to a psychological disorder or a procedure of the clinical investigation.

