2.3. Benefit/Risk Assessment

2.3.1. Risk Assessment

D. C. I.D. C. C. C.D. C. D. C. L. M. C.								
Potential Residual Risk of Clinical Significance	Summary of Data/Rationale for Risk	Mitigation Strategy (Control Measure)						
	dCBT-PF							
Negative wellbeing / distress (ADE or ASADE)	Negative wellbeing /distress have been observed in patients after initiation of CBT	Eligibility criteria to safeguard that population will exclude patients at high risk for negative impact on wellbeing/distress (i.e., patients with a history of hospital admissions due to suicidal behavior or attempts (self-reported) or patients with a diagnosis of major depressive disorder (self-reported) Questions will be asked to enquire about any potential adverse events, and depending on the response, the appropriate action will be taken to ensure that the well-being of the subject is safeguarded (including reporting and follow-up of any AEs and ADEs) The dCBT-PF will include disclaimers to encourage subjects to contact their PCP or National suicide hotline, if there is a need for professional support						

No other residual risks are anticipated to cause ADEs.

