8.4. Adverse Events, Serious Adverse Events, and Other Safety Reporting

The definitions and reporting requirements for AEs, ADEs, SAEs, and SADEs can be found in Appendix 2 (see Section 10.2).

AEs will be reported by the subject and will be classified as AEs, ADEs, SAEs, and SADEs according to the definitions provided in Section 10.2. ADEs and SADEs can only occur in the dCBT-PF group as there are no intervention in the control group. All ADEs, SAEs and SADEs should be reported in the CRF. Aes, not fulfilling the definition of an ADE, SAE, and SADE, should only be reported if they are related to a psychological disorder or a procedure of the clinical investigation.

The investigator and any qualified designees are responsible for detecting, documenting, and recording events that meet the definition of an AE, ADE, SAE, or SADE. They further remain responsible for following up on AEs, ADEs, SAEs, or SADEs.

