9.3.4. Safety Analyses

Safety analysis will be based on the safety set.

AEs will be analyzed using quantitative and qualitative measures. AEs will be summarized by treatment group for all AEs, ADEs, SAEs, SADEs (unanticipated SADE (USADE), or anticipated SADE (ASADE)), deaths, AEs leading to discontinuation of dCBT-PF or to withdrawal from investigation, and device deficiencies. AEs will be coded using the Medical Dictionary for Regulatory Activities (MedDRA) and summarized by system organ class and preferred term for each treatment group. ADEs and SADEs only applies to the dCBT-PF therapy group.

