10.2.5. Recording and follow-up on of AE, ADEs, SAEs or SADEs

AE, ADE, SAE, SADE and device deficiency recording

- AEs/ADEs/SAEs/SADEs will be collected from signing the ICF. Device deficiencies will be collected from start of dCBT-PF use.
- A pre-existing medical condition should be reported if the condition increases in severity (e.g. from non-severe to severe).
- At each visit the subject should be asked about AEs in an objective manner, e.g.: "Have you experienced any problems since the last visit?".
- All AEs/ADEs/SAEs/SADEs should be followed until they have reached a final outcome (Resolved, resolved with sequelae, death) or the subject's participation in the trial ends, whichever comes first.
- The outcome "Ongoing" can be used as the final outcome for events that are not expected
 to resolve over time.
- ADEs, SADEs should be followed on a regular basis according to the investigator's clinical judgment until a final outcome has been established.

Causality of AEs (relationship to device or procedure)

- Not related
- Possible
- Probable
- Causal

The AEs fulfilling causality criteria possible, probable and casual are all classified as ADEs

Event status

The Investigator is obliged to record the most appropriate outcome using the following categories:

- Resolved
- Resolved with sequelae
- Ongoing
- Death

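### The visible plan does not separate unreported lack of efficacy from reportable worsening of anxiety, and no safety table counts deterioration independently of the site's label

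*Combined protocol and SAP*

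**What the plan says.** All references are to the combined protocol and SAP.

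- **Exemption (10.2.1).** "Lack of efficacy per se will not be reported as an AE or SAE. Such instances will be captured in the efficacy assessments".
- **Worsened conditions (10.2.5).** "A pre-existing medical condition should be reported if the condition increases in severity (e.g. from non-severe to severe".
- **Psychological events (8.4, repeated in 10.2.1).** Adverse events that are not ADEs, SAEs or SADEs "should only be reported if they are related to a psychological disorder or a procedure of the clinical investigation". Psychological events are therefore within what sites must report.
- **Anticipated risk (2.3.1).** "Negative wellbeing /distress have been observed in patients after initiation of CBT". The section expects no other residual risk to produce ADEs.
- **Population and outcome (5, 9.3.2).** Entry requires a GAD-7 score of at least 5. The primary analysis is an adjusted mean difference in GAD-7 change at Week 9.
- **Who knows the allocation (6.3).** Subjects, investigators, the sponsor and vendor staff know it; the HAM-A rater is blinded. Controls receive no treatment.
- **Safety analysis (9.3.4).** "AEs will be summarized by treatment group for all AEs, ADEs, SAEs, SADEs", with deaths, events leading to discontinuation or withdrawal, and device deficiencies.

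**The concern.** The condition treated, the primary outcome and the one anticipated harm overlap. When a subject's anxiety rises during the trial, the site has to decide whether the treatment has not worked or the subject has got worse. The first is left to the efficacy assessments and the second is an adverse event. The visible text gives no criterion for that decision.

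The safety objective in Section 3 compares dCBT-PF with control, and the classification is made by staff who know the arm. Lack of efficacy has a natural meaning only where there is a treatment, so the exemption fits one arm better than the other. If the label is applied differently by arm, the comparison of the one anticipated harm is distorted. The efficacy analysis is not built to show it either, because a mean change at one visit can stay favourable while a minority deteriorates.

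**Working it through.** No figure in the plan depends on this rule, so there is nothing to reproduce. The sample-size text is not available, so every effect size, SD and event rate below is an assumption.

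**1. The sections applied to one case.** Take a dCBT-PF subject whose GAD-7 goes from 6 to 13 (+7).

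| Section | Reading open to the site | Result |
|---|---|---|
| 10.2.1 | The treatment is not working | Not reported |
| 10.2.5, severity | Pre-existing anxiety is more severe | Reported |
| 8.4 | Event related to a psychological disorder | Reported as an AE |
| 10.2.5, causality | Relation to the device at least possible | Reported as an ADE |

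The only severity guide in 10.2.5 is an example, and it is tied to no scale. The protocol does not link it to the GAD-7 bands in 8.2.1 (5-9, 10-14, 15 and above). A site that made that link itself would find that even a rise from 5 to 14 (14 - 5 = 9 points) does not reach severe. On the waitlist, the first row has no obvious counterpart and the last cannot occur, because 8.4 confines ADEs to the dCBT-PF group.

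**2. What a mean difference can hide.** Inputs: 250 subjects at most, randomised 1:1, so 250 / 2 = 125 per arm. Assume a fraction f of the dCBT-PF arm worsens by 5 points relative to control and the rest gain 3.

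Mean difference = (1 - f) x (-3) + f x 5

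- f = 2%: 0.98 x (-3) + 0.02 x 5 = -2.84; 0.02 x 125 = 2.5 subjects worse
- f = 5%: 0.95 x (-3) + 0.05 x 5 = -2.60; 6.25 subjects
- f = 10%: 0.90 x (-3) + 0.10 x 5 = -2.20; 12.5 subjects

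At f = 10%, power for a favourable primary result (two-sided 5%) is 0.99, 0.94 or 0.83 for an SD of 4, 5 or 6. With no worsening it is 1.00, 1.00 or 0.98.

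The result depends on the assumed benefit. With a gain of 2 points, 0.90 x (-2) + 0.10 x 5 = -1.30, and power is 0.73, 0.54 or 0.40. Masking is possible, not certain.

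**3. How sensitive the AE comparison is to labelling.** At 125 per arm, power to separate event rates of 10% and 2% is 0.76; for 5% and 2% it is 0.25. The step from 10% to 5% on one arm is 12.5 - 6.25 = 6.25 subjects. About six relabelled events would move the comparison from reasonable power to little.

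**4. What a label-free count must cover.** GAD-7 runs from 0 to 21. A subject in the severe band (15-21) cannot move up a band, and 21 - 5 = 16, so only baseline scores of 15 and 16 can rise by 5. Five of the seven severe scores (17 to 21) could meet neither a band criterion nor a 5-point criterion. A band shift alone is also uneven: 9 to 10 changes band, 5 to 9 does not. Band shifts and the full distribution of increases are both needed.

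**The case against.** The strongest reply is that the sections fit together as written. Lack of efficacy as such means failure to improve, worsening is something else, and 10.2.5 and 8.4 cover worsening. That reading is fair. A reader might infer that the plan contradicts itself; it does not, because no section requires lack of efficacy to be reported. What is missing is the boundary.

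A reader might also infer that harm would disappear into the efficacy mean. The documents do not support that:

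- Table 2 schedules a wellbeing and distress question at all four post-baseline visits, and 2.3.1 ties safety questioning to AE and ADE reporting.
- Section 7.2 withdraws subjects with significant new or worsened distress, and 9.3.4 and 9.3.5 tabulate AEs leading to withdrawal and reasons for withdrawal by group.
- Section 9.3.1 lists all efficacy and safety data, and the monitoring committee (10.1.5.1) reviews both kinds.

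These safeguards stand. They do not remove the gap: the AE tables carry the site's label, and a listing is not a comparison of arms. Subjects withdrawn for distress may also have Week 9 GAD-7 imputed (9.3.2), although imputation uses their earlier scores and a tipping-point analysis is planned.

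A third inference is that harm would be under-counted on dCBT-PF. That is not shown. The exemption pulls that way, but any event judged even possibly device-related becomes an ADE, and every ADE must be reported, which pulls the other way.

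Two limits also stand. Section 2.3.1 names negative wellbeing or distress, so treating rising anxiety as an instance of it is a reasonable inference, not the plan's wording. And some exploratory endpoints are redacted, Section 9 leaves detail to the SAP, and 7.2 cites a separate process document. A criterion or a deterioration analysis may exist in one of these.

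**Conclusion.** The point holds as an undefined boundary. The visible text does not say when rising anxiety is unreported non-response and when it is a reportable worsening. The decision rests with staff who know the allocation, so labelling could differ by arm in an unknown direction. Section 9.3.4 has no count of deterioration that is free of that label.

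The primary efficacy inference is not at risk. The weakness is in the comparison of the one anticipated harm, where on the assumed rates about six events in 125 would matter. That size rests on full recruitment of 250 and on assumed benefits, SDs and event rates; none is a figure from the plan. The change is worth making because it is cheap.

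**What to change.** 1. **Wording.** Reconcile 10.2.1 with 8.4 and 10.2.5 so that one rule, fixed in advance and applied alike in both arms, separates absence of improvement from worsening.
2. **Table.** Add to 9.3.4 a descriptive by-arm shift table of GAD-7 severity band (8.2.1) from baseline to Weeks 3, 6, 9 and 12 and to the worst post-baseline value. Beside it, give the by-arm distribution of increases from baseline, so that subjects already in the severe band are covered. Use observed scores and show the number assessed at each visit, so that subjects who withdraw contribute what they have. These are analysis cuts, not clinical rules.

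Controls get access to the device only after Week 12 (6.5), so the arms remain comparable over the whole table. GAD-7 is self-reported by subjects who know their arm, so the table is free of site labelling but not of subject expectation.

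Cost: a short text change, one extra table from data already collected, and possibly a few more recorded AEs. If a redacted endpoint or the SAP already provides such a count, a cross-reference in 9.3.4 is enough for item 2.

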10.2.2. Definition of ADE (Adverse Device Effect)

ADE Definition

An ADE is an AE related to the use of the investigational medical device.

Includes:

- Events resulting from insufficient or inadequate instructions for use, deployment, installation, operation, or any malfunction (0) of the investigational medical device
- Events resulting from use error or intentional misuse
- Events related to comparator if comparator is medical device

10.2.3. Definition of SAE (Serious Adverse Event)

An SAE is defined as any untoward medical occurrence that meets one or more of the criteria listed:

a. Results in death

b. Serious deterioration in the health of the subject, user or other persons as defined by one or more of the following:

A life-threatening illness or injury

A permanent impairment of a body structure or a body function including chronic disease

Inpatient hospitalization* or prolonged hospitalization

Medical or surgical intervention to prevent life-threatening illness or injury, or permanent impairment to a body structure or body function

Note*:

Planned hospitalization for a pre-existing condition, or a procedure required by CIP without serious deterioration in health, is not considered a SAE

c. Foetal distress, foetal death, a congenital abnormality, or birth defect including physical or mental impairment.

10.2.4. Definition and categorization of SADEs (Serious Adverse Device Effects)

SADE definition

A SADE is an adverse event effect (ADE, 10.2.2) that has resulted in any of the consequences characteristic of an SAE)

SADE is categorized as:

- ASADE anticipated SADE, or
- USADE unanticipated SADE

USADE definition from 21 CFR part 812:

Any SADE on health or safety or any life-threatening problem or death caused by, or associated with, a device, if that effect, problem, or death was not previously identified in nature, severity, or degree of incidence in the investigational plan or application (including a supplementary plan or application), or any other unanticipated serious problem associated with a device that relates to the rights, safety, or welfare of subjects.

10.2.5. Recording and follow-up on of AE, ADEs, SAEs or SADEs

AE, ADE, SAE, SADE and device deficiency recording

- AEs/ADEs/SAEs/SADEs will be collected from signing the ICF. Device deficiencies will be collected from start of dCBT-PF use.
- A pre-existing medical condition should be reported if the condition increases in severity (e.g. from non-severe to severe).
- At each visit the subject should be asked about AEs in an objective manner, e.g.: "Have you experienced any problems since the last visit?".
- All AEs/ADEs/SAEs/SADEs should be followed until they have reached a final outcome (Resolved, resolved with sequelae, death) or the subject's participation in the trial ends, whichever comes first.
- The outcome "Ongoing" can be used as the final outcome for events that are not expected
 to resolve over time.
- ADEs, SADEs should be followed on a regular basis according to the investigator's clinical judgment until a final outcome has been established.

Causality of AEs (relationship to device or procedure)

- Not related
- Possible
- Probable
- Causal

The AEs fulfilling causality criteria possible, probable and casual are all classified as ADEs

Event status

The Investigator is obliged to record the most appropriate outcome using the following categories:

- Resolved
- Resolved with sequelae
- Ongoing
- Death

10.2.6. Device deficiencies

Device deficiency definition

Device deficiency is inadequacy of a medical device with respect to its identity, quality, durability, reliability, usability, safety, or performance.

Device deficiencies include:

- Malfunctions (failure to perform in accordance with its intended purpose when used according to instructions)
- Use errors (inability of user to use the device properly, which user might be aware or unaware about)
- Inadequacy in the information supplied by manufacturer including labelling related to investigational medical device or the comparator

10.4. Appendix 4: Abbreviations

ACT Acceptance & Commitment Therapy

AE Adverse event

ADE Adverse device effect

ALAT Latin American Thoracic Association

ANCOVA Analysis of covariance analysis

ASADE Anticipated serious adverse device effect

ATS American thoracic society

CBT Cognitive behavioral therapy

CIP Clinical investigation plan

CRC Clinical Research Coordinator

CRF Case report form

CT Computed Tomography

dCBT Digital cognitive behavioral therapy

dCBT-IPF Digital cognitive behavioural therapy in idiopathic pulmonary

fibrosis (DTx name applicable for the pilot phase)

dCBT-PF Digital cognitive behavioural therapy in pulmonary fibrosis

Dtx Digital therapeutics

ePRO Electronic patient reported outcomes

ERS European respiratory society

FVC Forced vital capacity

GAD-7 7-item generalized anxiety disorder questionnaire

GCP Good clinical practice

HAM-A Hamilton anxiety rating scale

HRCT High-Resolution Computed Tomography

ICF Informed consent form

IRB institutional review board

IPF Idiopathic pulmonary fibrosis

ISO International organization for standardization

ITT Intention to treat

JRS Japanese respiratory society

K-BILD King's brief interstitial lung disease questionniare

MDR Medical device regulation

MedDRA Medical Dictionary for Regulatory Activities

PCP Primary Care Provider

PI Principal Investigator

SAE Serious adverse event

SADE Serious adverse device effect

SoA Schedule of activities

[figure not shown]
SD Standard deviation

USADE Unanticipated serious adverse device effect

11. Amendment History

Amendment Summary of Changes Table

[figure not shown]
DOCUMENT H	IISTORY	
Document	Description of Change	Rationale for changes

Document	Description of Change	Rationale for changes	Applicable for sections
	Adjustment for the	To reflect the above	1.2, 8.1, 8.1.1., 8.1.2.2, 8.2.2
	assessment for the pivotal	listed changes and ensure	
	phase.	a better operational flow.	

	T	
	Text for sample size	
	determination updated	
	after FDA advise.	
Section		
Section		

Document	Description of Change	Rationale for changes	Applicable for sections
			_

12. References

